3.1.3 Multiple Comparisons/Multiplicity

Multiplicity adjustment is not planned for this phase 2 study.

3.1.4 Multi-centre Studies

No per centre (where the term ‘centre’ defines each investigator site) summaries or analyses is planned.

3.2 Analysis Populations

The analysis populations are defined in [Table 2](#).

Table 2: Analysis Populations

Population	Description
Enrolled	All subjects who sign the informed consent form.
Full Analysis Population	All subjects from cohorts 2 and 3 who are randomized and receive any study drug. Subjects are evaluated according to the treatment assigned at randomization. The Full Analysis Population will be used for all analyses of demographic baseline characteristics and efficacy data.
Per Protocol Population	A subset of the Full Analysis Population consisting of all subjects who receive the additional treatment with dapagliflozin post Week 12 and do not violate the terms of the protocol in a way that may affect the primary efficacy endpoint significantly (relevant protocol deviations (IPDs)). The relevant IPDs are reported in Section 3.3.2.
Safety Analysis Population	All subjects from cohorts 2 and 3 who are randomized and receive any study drug. Subjects are evaluated according to the actual treatment they received. The Safety Analysis set will be used for all safety analyses.
PK population	All subjects in the Full Analysis Population who have at least one detectable MEDI3506 serum concentration measurement post-treatment. The PK Analysis set will be used for all PK analyses.

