The study was started in November 2019 as a Phase 2a study and it was paused due to COVID-19 pandemic by March 2020. It was resumed in July 2020, and then endured several amendments where additional doses of MEDI3506 and the add-on of Dapagliflozin in the second half of the 6-month treatment period are introduced. Therefore, the study consists of two periods, where Period 1 is without Dapagliflozin and Period 2 is with Dapagliflozin. Accordingly, several cohorts of participants can be defined upon the evolution of the trial design as illustrated in [Table 1](#). Cohort 1 which are divided in two groups a and b, are subjects who have started on the Phase 2a. Cohort 1a participants were discontinued and did not have the opportunity to complete 6-month treatment due to COVID-19 pandemic. Participants in Cohort 1b were enrolled after the study was re-started and had the opportunity to complete 6-month treatment. These subjects will continue on treatment with MEDI3506/placebo without dapagliflozin. About 24 participants were randomized in Cohort 1 and 19 of them were discontinued when the study was paused. Cohort 2 are subjects who have started on the Phase 2a study but have not completed 12 weeks of treatment prior to Amendment 2. They were transitioned to the Phase 2b study and given dapagliflozin starting on Day 85 (Week 12). Finally, Cohort 3 are subjects who will enrol in ongoing Phase 2b study.

Table 1: Cohort of study participant by randomization scheme and active treatment regiment

Cohort	Randomization Scheme 1 (R1)	Randomization Scheme 2 (R2)	Active Treatment Regiment	
			6-month MEDI3506 monotherapy	MEDI3506 mono in 1 st 3 mons, MEDI3506 + Dapa in 2 nd 3 mons.
1a*	X		X	
1b*	X		X	
2	X			X
3		X		X

R1 = Randomization scheme for MEDI3506 60 mg, 300 mg, and matching placebo; R2 = Randomization scheme for MEDI3506 30 mg, 60 mg, 120 mg, 300 mg, and matching placebo.

* Participants in Cohort 1a were discontinued and did not have the opportunity to complete 6-month treatment due to COVID-19 pandemic. Participants in Cohort 1b were enrolled after the study was re-started and had the opportunity to complete 6-month treatment.

Should be noted that the method and the analysis details described in this document will be considered for Cohort 2 and 3. Cohort 1 will be summarized separately with some descriptive summary statistics and listing.

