3.6 Safety Analyses

The analyses of the safety endpoints will be performed using the Safety Analysis Population for data cut-off at day 85 and all data available beyond day 85. The evaluations will be descriptive in nature, and observed differences will be evaluated for medical relevance. No formal statistical comparisons will be performed for the safety summaries.

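### The Safety Analysis Population excludes dosed Cohort 1 participants from every by-arm safety table the SAP specifies, and the separate Cohort 1 report promised for them has no defined set and no stated safety content

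*SAP*

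**What the plan says.** SAP Section 3.2, Table 2, defines the Safety Analysis Population as: "All subjects from cohorts 2 and 3 who are randomized and receive any study drug. Subjects are evaluated according to the actual treatment they received". It adds: "The Safety Analysis set will be used for all safety analyses". Section 3.6 repeats the choice: "The analyses of the safety endpoints will be performed using the Safety Analysis Population". Section 3.7 bases the anti-drug antibody analysis on the safety population as well. Appendix A 3 runs the interim safety analysis on the same subjects as the Full Analysis Population, which Table 2 also restricts to Cohorts 2 and 3.

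The Introduction (Section 1) describes the group left out: "About 24 participants were randomized in Cohort 1 and 19 of them were discontinued when the study was paused". Its Table 1 places Cohort 1 under the same randomisation scheme as Cohort 2: "R1 = Randomization scheme for MEDI3506 60 mg, 300 mg, and matching placebo". On reporting, the Introduction says "Should be noted that the method and the analysis details described in this document will be considered for Cohort 2 and 3" and then "Cohort 1 will be summarized separately with some descriptive summary statistics and listing".

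Table 2 defines no Cohort 1 analysis set. No later section says what the separate summary contains.

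**The concern.** A safety population normally takes in everyone who was randomised and dosed, whatever happened to the design afterwards. Here the safety set carries the same cohort restriction as the efficacy set. For Week 24 efficacy the restriction has an evident reason: Cohort 1 was not given dapagliflozin in the second half of treatment. For safety before dapagliflozin starts, that reason does not apply.

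The events that matter most are rare ones: death, serious hypersensitivity, serious infection and progression of heart failure. They are judged on small counts. The SAP's interim criteria (Appendix A 3, Table 4) refer to differences of 3 to 5 patients for fatal infections and for heart failure deaths, and label those cut-offs as approximate. One such event in a dosed Cohort 1 participant would not appear in the by-arm tables or the MEDI3506-overall column described in Sections 3.6.1 to 3.6.4. Whether it appeared by arm elsewhere would depend on outputs that the SAP does not itemise.

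**Working it through.** The SAP gives no figure for the effect of this exclusion, so the check is mainly a comparison of sections. The arithmetic only sizes the group.

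**1. Does the dapagliflozin difference justify exclusion up to Day 85?**

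- Regimen: Table 1 of the Introduction gives Cohorts 2 and 3 MEDI3506 (or placebo) alone for the first three months. Cohort 2 starts dapagliflozin on Day 85. Cohort 1 receives MEDI3506 or placebo without dapagliflozin throughout. Until Day 85 the planned regimens are alike.
- Randomisation scheme: Cohort 1 is under R1, and so is Cohort 2. The safety set already pools Cohort 2 (R1) with Cohort 3 (R2), so being under R1 is not a ground for exclusion.
- Data cut: Section 3.6 already plans safety output at a Day 85 cut-off. Adding Cohort 1 there needs no new method.
- Objective: Section 2.1.2 includes safety and tolerability across Periods 1 and 2, and the Introduction defines Period 1 as the part without dapagliflozin. Cohort 1 data to Day 85 bear on that objective.

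None of these supports leaving Cohort 1 out before Day 85.

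**2. How large is the group?**

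Inputs: about 24 randomised, 19 of them discontinued at the pause (Introduction); planned arms 95, 95, 95, 140 and 140 (Section 2.4). The planned arms reproduce the stated total: 3 × 95 + 2 × 140 = 565.

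- Share of all randomised, if 565 excludes Cohort 1: 24/(565 + 24) = 24/589 = 4.1%.
- Discontinued at the pause: 19/24 = 79%.
- Share of a pooled arm, assuming 8 per arm (the R1 ratio is not given): 8/(95 + 8) = 7.8% of 60 mg, and 8/(140 + 8) = 5.4% of each of 300 mg and placebo. With 6 to 12 per arm the range is 5.9% to 11.2% for 60 mg (6/101 to 12/107) and 4.1% to 7.9% for 300 mg and placebo (6/146 to 12/152). For 30 mg and 120 mg it is 0%, because R1 had neither dose.

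**3. Could it matter for rare events? (illustration only)**

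If R1 was 1:1:1 and everyone was dosed, 24 × 2/3 = 16 participants received MEDI3506. The chance of at least one event is 1 − (1 − p)^16 for an assumed per-subject risk p:

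- p = 1%: 1 − 0.99^16 = 15%
- p = 2%: 1 − 0.98^16 = 28%
- p = 5%: 1 − 0.95^16 = 56%

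The SAP gives no event risk, so these values of p are assumptions. With most of Cohort 1 stopped early, the risk accrued per participant may be lower than in a full course.

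**The case against.** The strongest reply is that the split is deliberate and disclosed. The Introduction limits the SAP's methods to Cohorts 2 and 3 and sends Cohort 1 to separate reporting. Read that way, the reference in Table 2 to all safety analyses means those done under these methods. Section 1 also leaves table templates and specifications to a statistical programming plan that is not at hand, and the Cohort 1 outputs may be listed there.

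This stands to a considerable degree. A reader might infer that Cohort 1 deaths, SAEs and AESIs will go unreported, or will be missing from every by-arm display. The document does not support that. It promises a summary and a listing, and nothing says that these omit safety or are not by arm. What remains is that the SAP does not commit to that content.

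A second reply concerns pooling. About 79% of Cohort 1 was stopped at the pause. Section 3.6.1 counts each subject once per term, and rates per patient-year appear only in Appendix A 3. Adding Cohort 1 to the main tables would put mostly truncated exposure into three of the five arms and could dilute crude incidence unevenly across doses. This also stands. It is a reason not to redefine the main safety population, but it does not count against a supportive table that shows exposure.

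A third reply is that the DSMB can review collected data by treatment during the study (Section 3.6.7). That covers oversight while the trial runs. It does not settle what the final report shows.

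A reader might also infer that Cohort 1b alone received MEDI3506 without dapagliflozin after Week 12. That holds for the planned regimens in Table 1 only. Section 2.3 allocates dapagliflozin to eligible subjects, so some Cohort 2 and 3 participants may have gone without it.

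**Conclusion.** The point holds in a limited form. Dosed Cohort 1 participants are outside every by-arm safety table that the SAP specifies. The separate report promised for them has no analysis set and no stated commitment to deaths, SAEs or AESIs by arm. The dapagliflozin difference does not justify this for data up to Day 85.

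The group is small: about 4% of all randomised participants, on the assumption that the 565 does not already count Cohort 1. The figure of about 24 is the number randomised. The number dosed is not stated and could be lower, and the arm split is not stated either. The per-arm shares and event probabilities rest on assumed splits and risks and show only that an event in this group is plausible.

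The documents do not show that safety data are being withheld, and they do not require the main safety population to be redefined. They support a supportive analysis and a clear statement of what the Cohort 1 report will contain.

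**What to change.** Leave the Full Analysis Population and the main Cohort 2 and 3 safety tables unchanged. Then:

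1. Add to Table 2 an All-Treated Safety set: all randomised subjects in any cohort who received any study drug, by actual treatment. Reword the sentence on all safety analyses so that it is consistent with this set and with the Cohort 1 report.
2. On that set, produce supportive tables by arm and for MEDI3506 overall of deaths, SAEs, AESIs and AEs leading to discontinuation, for the period before dapagliflozin (to Day 85). Show exposure-adjusted rates next to the counts, because most of Cohort 1 had truncated exposure.
3. State that the separate Cohort 1 report gives the same events by arm, with the number dosed in each arm. It should include Cohort 1b after Week 12 and any later events within the treatment-emergent window of Section 3.6.1.

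The cost is SAP wording and a few extra tables. No new data are needed, and the efficacy analyses are not affected.

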3.3 Study Subjects

3.3.1 Subject Disposition and Completion Status

A summary of subject eligibility and randomization (including a summary of subjects randomised but not treated with double-blind investigational product) as well as treatment administered will be provided. In addition, disposition of subjects throughout the study with respect to completion of treatment and end of study will be provided.

A summary on randomization stratification factors will be provided, i.e., SGLT2i treatment history (with SGLT2i background, without SGLT2i background) and region (Japan, Rest of World) at randomization by treatment group and overall.

The number and percentage of participants with one or more disruptions due to COVID-19 pandemic will be presented by treatment group. A listing of all participants affected by the COVID-19 related study disruption by unique participant number identifier and by investigational site, and a description of how the individual's participation was altered, will be produced. COVID-19 related study disruptions can be:

1. Visit related (if visit is impacted by global/country situation, then contact mode will be specified);

2. Study drug related (if study drug action taken (except “Drug Withdrawn”) was impacted by global/country situation; study drug administration or location was impacted by global/country situation; who performed a study drug administration);
3. Concomitant medication related (if when treatment was stopped due to any global/country related situations i.e.: epidemic/pandemic, healthcare crisis etc.);
4. Discontinuation of study drug due to COVID-19 pandemic (if study drug action taken “Drug Withdrawn” was impacted by global/country situation);
5. Withdrawal from study (if primary reason for ending study is related to global/country situation).

3.3.2 Important protocol deviations

Important protocol deviations (IPDs) are a subset of protocol deviations that may significantly impact the completeness, accuracy, and/or reliability of the study data or that may significantly affect a subject’s rights, safety, or wellbeing (ICH E3 guidance). The category of IPDs for the study are:

1. Informed consent
2. Study conduct/procedures
3. Investigational product
4. Safety
5. Other reasons

The relevant IPDs are those that have the potential to affect the results of the primary efficacy endpoint. Therefore, the category of relevant IPDs for the study would be:

- Did not meet inclusion/exclusion criteria
- Did received prohibited medication before end of treatment
- Missed visit (we allow 1 missed visit. For IA any missed Visit before Day 85 would be relevant PD, but not for the Final Analysis if they attend the rest
- Did not provide UACR samples / samples were lost / samples were damaged

Details of the IPDs will be provided in the protocol deviation plan (PDP), which will be developed for the study. The method for identifying IPDs will be documented in the PDP. All blinded IPDs will be agreed prior to study unblinding by blinded study personnel. Unblinding IPDs (i.e. those that relates to study medication/dosing and which could

potentially unblind a reviewer to subject's treatment group) will be agreed by unblinded personnel.

The number and percentage of participants with at least one IPD, including and excluding COVID-19 related IPDs, will be summarised following the IPD categories for each study intervention group and overall. A listing of all identified IPDs will also be provided. All issues reported due to COVID-19 pandemic, regardless of whether the type of issue is considered a protocol deviation or not, will be listed separately.

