3.4.1.2 Primary Efficacy Analyses

The primary efficacy endpoint of change from baseline in UACR at Day 169 (Week 24) for each of the MEDI3506 treatment groups compared with the pooled placebo group will be analyzed based on the Per Protocol Population. For the intercurrent events, if a subject is lost to follow-up (EOT), discontinues treatment due to AE, or uses prohibited medication, the UACR data are treated as missing on or after the event and no imputation is performed. The primary analysis will use a mixed model repeated measures (MMRM) analysis with a restricted maximum likelihood (REML) approach without multiplicity adjustment. UACR will be log-transformed before entering the data in the MMRM analysis to alleviate the skewness of the data. The model will adjust for fixed effects of treatment, visit, and treatment-by-visit interaction, randomization stratification factors, baseline log UACR and baseline log UACR-by-visit interaction. Randomization stratification factors are with SGLT2i background or not, in Japan or rest of world.

To allow generality for the covariance structure for the repeated measures, the variance-covariance matrix will be assumed to be unstructured, i.e., purely data dependent, to model within subject errors. If the unstructured variance-covariance matrix will not fit, i.e., fail to converge, the following covariance structures will be utilized in the order of 1) heterogeneous toeplitz, 2) heterogeneous autoregressive of order 1, and 3) heterogeneous compound symmetry. The first (co)variance structure which does not have a convergence problem will be the one used for the analysis. If a structured covariance has to be used, the “sandwich” estimator of the variance covariance matrix of the fixed effects parameters will be used in order to deal with possible model misspecification of the covariance matrix. The denominator degrees of freedom will be calculated according to the Kenward-Roger method. Additionally, there will be no adjustment for multiplicity.

If none of the above models converge, the analysis will be altered to use an analysis of covariance (ANCOVA) with last observation carried forward (LOCF) imputation method implemented. Details of this analysis is provided in the [Section 3.4.5](#) for sensitivity analysis.

Additionally, all collected values of UACR will be listed.

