APPENDIX

The image shows the letters 'CCI' in a large, bold, red, sans-serif font. The letters are set against a solid black rectangular background. The 'C's are slightly open at the top and bottom, and the 'I' is a simple vertical bar.

A 3 Safety Analysis

Safety analysis will be based on the Interim Safety Analysis set. Selected safety outputs will be presented by treatment group and overall. The interim safety analysis will be performed

on the same subjects as the Full Analysis Population (FAP), but evaluated according to the actual treatment they received. If there is no dosing error, this is exactly the same population as the FAP.

The safety and tolerability criteria are defined and tabulated below. When either the Go or Amber criteria are met, it will be considered as acceptable.

Table 4: Safety and Tolerability Go/No Go Criteria

	GO in line with current safety profile	Amber change in safety profile with potential impact on label or development	Alert major impact on label of continued development
Overall Tolerability	Tolerability not an important barrier to adherence with < 10 % discontinuation due to AEs related to MEDI3506	Tolerability may impact adherence with $\geq 10 - 25$ % discontinuation due to AEs related to MEDI3506	Tolerability has a meaningful impact on adherence with ≥ 25 % discontinuation due to AEs related to MEDI3506
Hypersensitivity	No imbalance in serious anaphylactic reactions with base case (i.e. perfunctory) contraindication statement only	Increased frequency of serious hypersensitivity reactions that results in labelling beyond base case contraindication	Occurrence of major anaphylactic-type reactions or high frequency of hypersensitivity reactions that negatively impact benefit/risk assessment
Serious infections	No clinically meaningful imbalance in infections of any type, particularly severe intensity or serious events	Clinically meaningful increased frequency of nonserious infections and/or relatively increased frequency (5 – 10 patients more than placebo)* serious infections	Dose-dependent meaningfully increased frequency of serious infections (>10 patients on highest dose relative to placebo)* and a relatively increased frequency (3 – 5 patients on highest dose relative to placebo)* of fatal infections impacting the benefit/risk ratio of MEDI3506

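### The list of relevant deviations that defines the primary analysis set omits receipt of a MEDI3506/placebo treatment or dose other than the one assigned

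*SAP*

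**What the plan says.** SAP Section 3.4.1.2 states that the Week 24 UACR change in each MEDI3506 group "compared with the pooled placebo group will be analyzed based on the Per Protocol Population".

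Table 2 in Section 3.2 makes that set a subset of the Full Analysis Population. Members must have received dapagliflozin after Week 12 and must "do not violate the terms of the protocol in a way that may affect the primary efficacy endpoint significantly". It adds: "The relevant IPDs are reported in Section 3.3.2". For the parent population, Table 2 says: "Subjects are evaluated according to the treatment assigned at randomization". The Per Protocol row gives no other rule for assigning subjects to arms.

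Section 3.3.2 has three relevant parts:

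- Five general IPD categories, of which the third is investigational product.
- A definition, "The relevant IPDs are those that have the potential to affect the results of the primary efficacy endpoint", followed by "Therefore, the category of relevant IPDs for the study would be" and four items: failed eligibility; prohibited medication before end of treatment; missed visits, with one allowed; and UACR samples not provided, lost or damaged.
- A procedure under which some IPDs ("those that relates to study medication/dosing and which could" reveal the treatment group) are agreed by unblinded personnel.

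The section leaves the details of the IPDs, and the method of identifying them, to a protocol deviation plan.

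**The concern.** The list does not follow from the definition placed directly above it. Receiving a different dose, or placebo instead of active drug, plainly can affect the Week 24 UACR result. The section already treats such events as IPDs and says who agrees them, yet does not carry them into the relevant list. The primary set therefore has an explicit requirement for the add-on, dapagliflozin, but none that the randomized product was the one given.

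At stake are the four dose-versus-placebo comparisons. An active-arm subject given placebo, or a placebo subject given active drug, pulls the contrast towards zero. A subject given a higher dose than assigned may push that arm's estimate the other way if the effect rises with dose.

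The gap also affects how membership of the set is decided. If dosing deviations are to count, the SAP gives no rule for them and leaves their agreement to people who know the treatment.

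**Working it through.** **Step 1. Set the definition against the list.**

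| Source | Wrong treatment or dose covered? |
|---|---|
| General IPD categories (3.3.2) | Yes, under investigational product |
| Definition of a relevant IPD (3.3.2) | Yes, on its plain meaning |
| Four listed relevant categories (3.3.2) | No |
| General clause of the Per Protocol definition (Table 2) | Arguably, but it points to 3.3.2 |
| Intercurrent events (3.4.1.2, 3.4.1.2.3) | No: loss to follow-up, discontinuation due to AE, prohibited medication |

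Actual treatment is used only for the Safety Analysis Population and the interim safety set. On the latter, Appendix A 3 says: "If there is no dosing error, this is exactly the same population as the FAP". No provision moves a wrongly treated subject to another arm, or removes one, for the primary analysis.

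**Step 2. Reproduce the SAP's power figures, as context.** Inputs from Section 2.4: log-scale SD 1.0, one-sided alpha 0.05, a 30% reduction, and 125 (300 mg and placebo) or 85 (each lower dose) evaluable subjects.

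- Effect on the log scale: ln(1/0.7) = 0.3567.
- 300 mg: SE = √(1/125 + 1/125) = 0.1265. Power = Φ(0.3567/0.1265 − 1.645) = 88.0% (stated: at least 85%).
- Lower doses: SE = √(1/85 + 1/125) = 0.1406. Power = Φ(0.3567/0.1406 − 1.645) = 81.4% (stated: 80%).

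The stated figures hold. They neither support nor weaken this point, but they give a scale for Step 3.

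**Step 3. Illustrate the dilution.** The SAP gives no dosing-error rate, so this is assumption only. A share f of an active arm loses the whole effect (worst case) and is kept under the assigned dose. The apparent reduction is 1 − exp{(1 − f) ln 0.7}.

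| f | Apparent reduction | Power if kept, 300 mg / lower dose | Power if excluded, 300 mg / lower dose |
|---|---|---|---|
| 0% | 30.0% | 88.0% / 81.4% | 88.0% / 81.4% |
| 2% | 29.5% | 86.8% / 80.0% | 87.7% / 81.0% |
| 5% | 28.7% | 84.9% / 77.8% | 87.3% / 80.3% |
| 10% | 27.5% | 81.4% / 73.8% | 86.4% / 79.2% |

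For example, at f = 5%: 1 − exp(0.95 × −0.3567) = 1 − exp(−0.3388) = 28.7%. The last column assumes that the effect in the remaining subjects is unchanged by the exclusion.

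On the log scale the shift is 0.05 × 0.3567 = 0.018 or 0.10 × 0.3567 = 0.036. Against the lower-dose SE of 0.1406 that is about 0.13 or 0.25 of a standard error.

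**The case against.** Four objections deserve an answer.

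**The general clause in Table 2 already reaches gross dosing errors, and the protocol deviation plan may name them.** This stands in part. A reader might infer that a wrongly dosed subject is certain to stay in the set. The SAP does not support certainty, because Table 2's clause and the definition in 3.3.2 could both be read to exclude that subject, and the deviation plan is not shown. But Table 2 refers to 3.3.2 for the relevant IPDs, 3.3.2 states the categories itself, and only details and method are deferred. The text conflicts with itself, and the literal list keeps the subject in.

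**Missed doses are largely handled.** This also stands in part. A reader might infer that subjects who miss several doses freely remain per protocol. Product is given by site personnel, so missing more than one visit catches many missed doses. UACR is also set to missing on or after discontinuation due to AE or loss to follow-up. Two gaps remain: doses not given at attended visits, and visits missed before Day 85, which do not count at the final analysis if the rest are attended. Excluding on adherence after randomization is a debatable trade-off, so this point does not rest on it.

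**Keeping subjects under their assigned dose is defensible.** It is. A reader might suppose that the set is meant to show the effect of the dose as given, but the SAP nowhere says so. If retention is intended, it should be stated, because the definition of a relevant IPD now says otherwise.

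**Errors may be rare.** IXRS kit assignment, an unblinded product manager and an accountability log (Section 2.3) guard against them. The remark in Appendix A 3 explains when two populations coincide and is not evidence that errors are expected.

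**Conclusion.** The point holds for receipt of a treatment or dose other than the one assigned. The list in Section 3.3.2 is narrower than its own definition, and it feeds the primary analysis set through Table 2. Following it as written leaves such a subject in the primary comparison under the assigned arm.

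The size is unknown and may be nil. The figures of 28.7% and 27.5% rest on assumed error rates of 5% and 10% with total loss of effect, and the corresponding bias is a fraction of a standard error. Dilution is also not the only possible direction. The case for change is that a stated rule is inconsistent and cheap to repair. It does not depend on the primary result being shown to be distorted.

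**What to change.** In Section 3.3.2, add to the relevant IPDs: received a MEDI3506/placebo treatment or dose other than that assigned. Make Table 2 and the sentence on unblinded agreement consistent with it.

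Derive the item by program from IXRS assignment and dosing records. Fix the rule before unblinding, so that unblinded staff do not decide membership of the primary set case by case. The rule should say whether one wrong administration is enough. It should also say whether a wrong placebo volume counts, given that the placebo groups are pooled. The SAP offers no basis for either answer, so the sponsor must set both.

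In the same edit, the sponsor should state whether doses not given at attended visits also count. Either choice is open if made before unblinding.

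The cost is a few lines of SAP text and a derivation from assignment and dosing records. The downside is that a few more subjects leave the Per Protocol set on a post-randomization criterion.
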